Main REC	Main Research Ethics Committee
NHS R&D	National Health Service Research & Development
PI	Principle Investigator
QA	Quality Assurance
QC	Quality Control
Participant	An individual who takes part in a clinical trial
REC	Research Ethics Committee
SAE	Serious Adverse Event
SDV	Source Document Verification
SOP	Standard Operating Procedure
SSA	Site Specific Assessment
TMG	Trial Management Group
TSC	Trial Steering Committee

4 Summary/Synopsis

Title	The incidence of hospital acquired pneumonia in patients who undergo temporary tracheostomy with oromaxillofacial resection and reconstruction for head and neck cancer. Version 1 – 24.09.2021
Protocol Short Title/Acronym	HAP in temporary tracheostomy
Protocol Version number and Date	1 24.09.2021
Study Phase if not mentioned in title	Observational cohort
IRAS Number	295395
REC Reference	
Sponsor Reference	
Study Duration	7 months
Sponsor name	GSTT/KCL
Chief Investigator	[name]
Funder	N/A
Medical condition or disease under investigation	Oromaxillofacial surgery in head and neck cancer
Purpose of research	Retrospective data analysis identifying hospital acquired pneumonia in patients who undergo temporary tracheostomy with oromaxillofacial surgery and free flap reconstruction
Primary objective	Undertake an adequately powered, robustly designed observational cohort study that describes the rates of hospital acquired pneumonia in patients who undergo a tracheostomy and those that undergo overnight intubation during oromaxillofacial surgery for HNC.
Secondary objective (s)	To investigate whether smoking history, respiratory history (COPD, asthma) or size of tumour are associated with an increased risk of developing hospital acquired pneumonia.
Number of Subjects/Patients	193
Study Type	Observational cohort
Endpoints	January 2023
Main Inclusion Criteria	Patients who underwent oromaxillofacial resection with free flap reconstruction and tracheostomy from 1st January 2018 to 31st December 2018. Patients who underwent oromaxillofacial resection with free flap reconstruction and with overnight intubation from 1st January 2014 to 31st December 2014
Statistical Methodology and Analysis	A power calculation has been used to determine the sample size required for statistical analysis of data. Statistical significance for rates of HAP will be tested between the two groups. It is anticipated that

	
data will not normally distributed and non-parametric testing will be used (Mann Whitney U/Chi-square depending on data type. Odds ratios using logistic regression will be used to explore the risk factors for HAP in this scenario which have previously been indicated to have been smoking, respiratory history and tumour size.

Human Tissue Samples (if applicable)	n/a
Data collected/storage (if applicable)	n/a

4. Introduction

This study aims to explore the rates of hospital acquired pneumonia (HAP) in those that undergo temporary tracheostomy with oromaxillofacial surgery (OMFS) and free flap reconstruction for head and neck malignancy. The study also aims to identify risk factors that may be associated with developing a HAP in this patient cohort. This introduction provides a background to the study, outlining surgical management of these cancers, the risks and benefits associated with siting a tracheostomy. It outlines the importance of knowing the risks associated with tracheostomy placement which in turn could allow the exploration into interventions that may any risks identified.

4.1 Head and neck cancer incidence

Head and neck cancer (HNC) involves epithelial malignancies of the upper airway and digestive tract (e.g. oral and nasal cavities, paranasal sinuses, pharynx and Larynx). They are heterogeneous group of tumours and are the eighth leading cause of cancer in the United Kingdom (UK) (Ferlay et al. (2010)with an annual incidence rate of 12,422 new cases (Cancer Research UK 2016-2018). OMF cancer comprises of malignant tumours located within the jaw, face, mouth and neck. Owing to pattern of HNC spread, lymph node excisions within the neck, termed neck dissection, are often performed alongside excision of the primary tumour Bullock et al. (2019). OMF malignancy rates have risen by more than 30% since the 1990's (OCIU head and neck profiles) as a result an increasing number of patients are undergoing extensive surgical resections and gruelling oncological treatment regimes. OMF malignancy is commonly diagnosed around 70 years of age and 69% of cases are diagnosed in men (Cancer research UK 2016-2018). Lifestyle & environmental factors can significantly increase the risk of developing OMF cancer, smoking can increase the chance of developing OMF cancer by up to 91% and excessive alcohol consumption by up to 81%. Socioeconomic deprivation is also attribute to high OMF cancer rates, increasing the risk of developing OMF cancer by up to 64% in females and 101% in males (Huber & Dort, 2018). A number of co-morbidities affecting major organ systems are directly correlated with smoking, high alcohol consumption and social deprivation. This combined with the risks of major OMF surgery (OMFS) can result in high treatment complication rates, further adding to the complexity in managing this disease (Goepfert et al., 2017).

4.2 Head and Neck cancer treatment

HNC treatment can consist of one, or a combination of treatments that includes radiotherapy, chemotherapy, immunotherapy and/or surgery. The covariance between the health and fitness of the patient, and the site, type, and stage of cancer, determine the nature, duration, and intensity of treatment. Between 45-75% of patients undergo oral and maxillofacial surgery as their primary treatment (Cancer research UK 2015-17). Surgery includes removal of the tumour & surrounding nodes with free flap reconstruction using autogenous bone grafting from a secondary donor site to improve aesthetics, speech, and swallow function. Resection of tumours within the oral cavity and maxillofacial area significantly impact on the structures involved with breathing, mastication, speech, swallowing and cosmetic appearance (Wang, Fu, Liu, Liu, and Cao (2018). The location of these tumours means airway security during and after surgery is paramount. Reconstruction of these areas with free tissue transfer (bone and soft tissue) and microvascular surgery repairs the defect and with rehabilitation, restores function (Patel, Kim, and Ghali (2019). The magnitude of insult to these two surgical sites is considerable as is the risk of post-operative complications, further compounded by the patients' chronic medical and lifestyle co-existing conditions (McMahon et al., 2013).

4.3 Airway security during surgery

Airway security in OMFS is a subject of wide controversy and discussion (Goetz, Burian, Weitz, Wolff, and Bissinger (2019)), unlike other major head and neck surgery where tracheostomy insertion is necessary due to more extensive resections on more than one critical structure responsible for breathing, speaking, eating and drinking. Some units' preference is to insert a tracheostomy to maintain a secure airway during surgery (Marsh, Elliott, Anand, and Brennan (2009)). In contrast, others mitigate the risk associated with tracheostomy insertion by opting for overnight intubation either via endotracheal (ETT) or nasopharyngeal (NP) intubation (Singh, Sankla, & Smith, 2016; Singh, Sankla, and Smith (2016)). In the acute post-operative phase intraoral swelling can occlude the upper airway necessitating a means of airway security (Coyle, Shrimpton, Perkins, Fasanmade, and Godden (2012); (Goetz et al., 2019). The risk of catastrophic bleed and loss of perfusion resulting in flap loss is thought to be around 5% (Bianchi, Copelli, Ferrari, Ferri, and Sesenna (2009)); (Zubair et al. (2020)), however timely resolution is paramount, risk of morbidity or mortality increases in the instance of catastrophic bleed. In the event of flap loss, the surgical insult a patient receives for a second flap from another site increases the risk of post-operative complications, length of stay and functional recovery. Intraoral swelling can make emergency endotracheal intubation challenging, and insertion of emergency tracheostomy may be required (Coyle et al. (2012)). As such, OMFS management of intra and post-operative airway security in the UK is variable (Rogers, Russell, and Lowe (2017)).

4.4 Temporary tracheostomy insertion

Tracheostomy formation is more prevalent than either methods of intubation - a UK national survey observed that 69% (39/57) of maxillofacial units would "usually" or "almost always" insert a tracheostomy for uncomplicated free flap surgery, whilst 24% preferred ETT intubation to mitigate morbidity associated with tracheostomy insertion (Marsh et al. (2009)). This suggests that for HNC surgeons the dominant risk is airway security, which is best managed by tracheostomy formation despite the secondary risks created. The risks associated with tracheostomy insertion are widely acknowledged with reported complication rates between 8-45% (Margaret J Coyle et al. (2013)). They include tracheal stenosis, respiratory arrest due to tube blockage or displacement, haemorrhage, fistula, failure to decannulate, pneumothorax, injury to surrounding structures and hospital acquired pneumonia (HAP) (Coyle et al., 2013; Crosher, Baldie, and Mitchell (1997)). Tracheostomy complications can be life threatening and distressing for patients, and are associated with an increased length of stay and mortality. Pulmonary complications such as HAP in patients who undergo tracheostomy for all types of head and neck surgery are reported to be around 45% (Morton 1990). Patients who develop a HAP have a longer critical care and hospital stay. For example, Castling, Telfer, and Avery (1994) reported a 4 day admission to ICU and hospital LOS of 25 days compared to 2 and 14 days in those who did not develop a HAP. Increased care needs involving a number of specialist clinicians, equipment such as tracheostomy tubes, suction, methods of humidification and antimicrobial medications individually and collectively have financial implications for the cost of patient care. Rates of HAP specifically in OMFS is unknown, if such data was available and was found to be clinically or statistically significant in either the tracheostomy group or overnight intubation group work investigating methods to reduce the rate of HAP, such as early mobility or humidification would be justified.

4.5 Endotracheal and Nasopharyngeal intubation

Despite temporary tracheostomy insertion continuing to be the preferred choice for airway security, there is some evidence that the current approach might need to adapt; patient experience data has shown that given the choice, patients would avoid tracheostomy formation if possible (Nakarada-

Kordic, Patterson, Wrapson, and Reay (2018)). Furthermore there are studies demonstrating that patients who undergo these procedures can be safely managed with overnight intubation. M. J. Coyle et al. (2013), and Singh et al. (2016) both demonstrated that overnight ETT intubation was associated with a lower rate of HAP (10% vs 38% and 6% Vs 12% respectively), and shorter hospital length of stay (12.9 Vs 18.0 days and 20.4 Vs 27.2 days P=0.03 respectively). Despite these data demonstrating more favourable outcomes when compared with tracheostomy, standardised criteria to assess complication outcomes were not used increasing the risk of detection bias. Statistical integrity is also questionable due to absent power calculations or small sample sizes. As a result the evidence justifying intubation remains equivocal. However, anecdotally, the evidence supports the notion that not only will patients avoid the risks and morbidity associated with tracheostomy insertion, they will be able to speak cough and clear secretions independently sooner (Coyle 2012) which will positively impact their overall post-operative recovery and experience.

4.6 Patient experience

There are few papers that have reported on patient experience with a tracheostomy, however it is an emerging theme of interest. Sherlock, Wilson, and Exley (2009) explored the hospital experience of patients who had a temporary tracheostomy sited for medical or surgical reasons, conducting 8 semi-structured interviews over a 12-week period. Patients reported finding the physical and psychological effects more disturbing than expected; experiencing discomfort, fear, and frustration when attempting to talk, eat and drink, and during routine care-activities (e.g. suction to remove tracheostomy secretions). A study conducted by Rogers et al. (2017) using a multi-staged approach to record the experience of a patients who underwent tracheostomy during surgery for HNC reported similar findings. They conducted 15 semi-structured interviews, and used themes identified during these interviews to construct a postal questionnaire. The response rate was a respectable 69% (86/125) and found 60% of patients would “very much” avoid a tracheostomy if at all possible. Patients also reported they had “very much or “quite a bit” of a problem with tracheostomy communication, routine care, choking, discomfort, and sleeping. The Rogers et al (2017) study included selected comments from patients who underwent tracheostomy and included:

“Horrendous. I used to be a nurse with children and you don't realise what it is like. I would sooner be dead than go through it again. It is a horrible, fearful, horrendous feeling especially when coughing and sucking down the tracheostomy. It was difficult to get a comfortable position getting the oxygen, alright when removed, over quite quickly. You don't know what it is like unless you have had it done. The feeling of sucking out was awful”.

These findings support the notion that temporary tracheostomy should not be considered a minor or routine procedure and that the risk of life-threatening airway compromise should be balanced against the risks associated with tracheostomy as well as poor patient experience. However further work fully exploring the experience of patients who undergo temporary tracheostomy is needed and any outcomes that may improve experience such as specialist tracheostomy nurses and pre-operative patient counselling could be investigated.

4.7 Summary and the research problem

The association between lifestyle and environmental factors and increased risk of developing HNC cancer are widely acknowledged. Smoking, alcohol consumption, socioeconomic status and low mental wellbeing are important determinants and highly prevalent factors affecting the onset,

prognosis and recovery from HNC (McCarter et al. (2018)). Rates of morbidity and mortality are higher in those who present with co-morbidities associated with the above-mentioned risk factors.

There is some evidence in support of safely managing OMFS patients with overnight intubation, however work needs to be done to establish what patients are suited to either method of airway protection. Tracheostomy remains the method of choice for airway security during OMFS, despite demonstrated and assumed risks associated with insertion, the associated financial burden and emerging evidence reporting on poor patient experience. HAP remains a prevalent perceived risk in those that undergo tracheostomy and is associated with increased length of critical care, and hospital length of stay, morbidity, and mortality. There is a need to accurately identify and quantify HAP rates with both methods of airway protection in OMFS. If such data were available clinicians and patients could make informed decisions on the best method of airway protection for the surgical procedure they are undergoing. If rates were found to be high in either scenario, and any patient risk factors were associated with the development of a HAP, further work could explore what pre or post-operative interventions could be deployed to help reduce the risk of developing a HAP.

5 Trial objectives and purpose

Student MRes project

- To select patients according to a pre-defined set of inclusion and exclusion criteria
- Collect pre-determined quantitative data relevant to the study question using hospital medical records
- Describe patient demographic data and explore any relationship between these and the development of a HAP
- Assess rates of HAP using historical medical data and pre-defined criteria that identifies hospital acquired pneumonia
- Describe rates of HAP in patients who did not have a tracheostomy inserted for maxillofacial surgery with free flap reconstruction
- Describe rates of HAP in patients who did have a tracheostomy inserted for maxillofacial surgery with free flap reconstruction

6 Study design & Flowchart

6.1 Study Design

In 2017, a new maxillofacial surgeon was appointed to Guy's & St Thomas' NHS Foundation Trust who's preference was to insert a temporary tracheostomy for all patients undergoing oromaxillofacial surgery with free flap reconstruction. Prior to this there was a wide variation in case selection with the majority of patients undergoing overnight intubation. Since subsequent practice has now changed and all patients now undergo tracheostomy insertion within OMFS, a prospective design is not possible, therefore, a single site retrospective observational design will be adopted, allowing data from two cohorts of patients identified to be collected within a feasible timeframe dictated by the module deadlines. Electronic and paper notes of patients from cohorts before and after the change in maxillofacial surgical practice (2014 and 2018) will be screened.

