Participants will be identified by screening consecutive sets of case notes and electronic records for the years of 2014 (those before tracheostomy insertion was routine, therefore those who did not have a tracheostomy inserted) and 2017 (tracheostomy insertion was routine). Eligibility criteria includes all patients who underwent oromaxillofacial surgery with tracheostomy and free flap reconstruction. Only those with missing or unavailable data will be excluded. The PI is an employee of Guy's and St Thomas' NHS foundation trust (GSTT) and will be undertaking all aspects of data collection and recording. As employees of GSTT the CI and PI have undertaken all relevant information governance mandatory training permitting access to required data. The study will take place at a single site – Guy's & St Thomas' NHS Foundation Trust.

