7.1 Subject inclusion criteria

- Patients who underwent maxillofacial resection with free flap reconstruction and tracheostomy from 1st January 2018 to 31st December 2018.
- Patients who underwent maxillofacial resection with free flap reconstruction and with endotracheal intubation from 1st January 2014 to 31st December 2014
- Patients over the age of 18

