7.2 Subject exclusion criteria

- Patients who did not undergo maxillofacial resection with free flap reconstruction and tracheostomy from 1st January 2018 to 31st December 2018 – not relevant and will not answer the study question
- Patients who did not undergo maxillofacial resection with free flap reconstruction and with endotracheal intubation from 1st January 2014 to 31st December 2014 - not relevant and will not answer the study question
- Patients under the age of 18

8 Study procedures

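### The tested HAP contrast sets 2014 patients chosen for intubation against a 2018 cohort with routine tracheostomy, so case selection, calendar period and surgeon are mixed with airway method, with no adjustment stated

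*Combined protocol and SAP*

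**What the plan says.** Section 6.1 bases the design on a change of practice: "In 2017, a new maxillofacial surgeon was appointed", whose preference was tracheostomy for every free flap case. Of the time before, it says "Prior to this there was a wide variation in case selection with the majority of patients undergoing overnight intubation". Of the time after, it says "all patients now undergo tracheostomy insertion within OMFS".

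Section 7 describes the 2014 patients differently: "those before tracheostomy insertion was routine, therefore those who did not have a tracheostomy inserted".

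The formal criteria in section 7.1 admit "Patients who underwent maxillofacial resection with free flap reconstruction and with endotracheal intubation from 1st January 2014 to 31st December 2014" and "Patients who underwent maxillofacial resection with free flap reconstruction and tracheostomy from 1st January 2018 to 31st December 2018". Section 7.2 excludes "Patients who did not undergo maxillofacial resection with free flap reconstruction and with endotracheal intubation from 1st January 2014 to 31st December 2014" as not relevant to the question. A 2014 patient who had a tracheostomy is therefore dropped.

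Section 11.1 powers the study on an odds ratio of 2.33 with one binary variable for cohort. Section 11.2 tests HAP rates between the two groups and uses logistic regression to explore smoking, respiratory history and tumour size as risk factors. It does not say that the cohort contrast will be adjusted for them. Section 10.1 also collects age, gender, cancer site, stage, surgery type, neck dissection and flap site, and gives them no role in adjustment.

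Section 4.7 says that with such data "clinicians and patients could make informed decisions on the best method of airway protection".

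**The concern.** A before-and-after comparison is attractive here because surgeon preference, not patient risk, changed the airway method. That advantage depends on taking everyone from both years. The eligibility rules take everyone, in effect, from 2018, but from 2014 only those selected for intubation. Patients of the kind given a tracheostomy in 2014 are missing or under-represented in one arm and present in the other.

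There is a second, separate problem. Every retained 2014 patient is intubated and every retained 2018 patient has a tracheostomy, so airway, calendar year and change of surgeon are a single variable in the data.

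If the 2014 selection was related to HAP risk, or if HAP rates moved between 2014 and 2018 for other reasons, the test can show a difference when airway method has no effect, or hide a real one. The result would then be a poor basis for the choice of airway, which is the use named in section 4.7.

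**Working it through.** **Inputs.** From section 11.1: total 193, odds ratio 2.33, 30% HAP in the 2014 cohort, 41% of patients from 2018, 80% power, two-sided 5%. (Section 11.1 labels the 2018 cohort as intubated, which conflicts with section 7.1; I use 41% as the 2018 share.) The documents give no 2014 tracheostomy share *f*; since the majority were intubated it must be below 50%. They also give no HAP risk *r* for those patients. Both are assumed below.

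**The plan's own figure.** The 2018 odds are 2.33 × 0.30/0.70 = 0.9986, so the 2018 rate is 0.9986/1.9986 = 49.96%. The pooled-variance two-proportion formula with ratio 0.41/0.59 and no continuity correction gives 114 patients from 2014 and 79 from 2018, total 193. The arithmetic holds; the issue is what the contrast estimates.

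**Can the retained data separate airway from period?** No. Among the 193, the airway indicator and the year indicator are the same column (114 zeros, 79 ones). With an intercept the design matrix has rank 2 for 3 columns, so no model fitted to these patients can split them.

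**Selection alone.** Assume no airway effect, no period effect, the same case mix in both years, and 30% HAP in the 2014 intubated patients. Then

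- expected 2018 rate p = 0.30(1 − f) + r·f
- spurious OR = [p/(1 − p)] / [0.30/0.70]

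For example, with r = 45% and f = 20%: p = 0.24 + 0.09 = 0.33, and OR = 0.4925/0.4286 = 1.15. The last column is the exact probability, over all outcomes with 114 and 79 patients, of a significant Pearson chi-square with HAP higher in 2018. With no bias it is 2.65%.

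| r | f | 2018 rate | Spurious OR | False 'tracheostomy worse' |
|---|---|---|---|---|
| 20% | 20% | 28% | 0.91 | 1.3% |
| 20% | 40% | 26% | 0.82 | 0.5% |
| 45% | 20% | 33% | 1.15 | 6.7% |
| 45% | 40% | 36% | 1.31 | 14.3% |
| 60% | 20% | 36% | 1.31 | 14.3% |
| 60% | 40% | 42% | 1.69 | 40.9% |

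A second model selects 2014 patients for tracheostomy by a risk factor (assumed: 40% of patients high-risk, selection OR 3 to 10, HAP OR 2 to 4, f from 10% to 49%). It gives spurious ORs of only 1.02 to 1.42.

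**Period or surgeon alone.** With no airway effect and no selection, a period OR of 1.25, 1.5 or 2.0 gives a significant result towards more HAP in 2018 about 11%, 26% or 63% of the time.

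**What including the 2014 tracheostomy patients buys.** Keeping 114 intubated patients, their number is 114f/(1 − f): about 28 at f = 20% and 76 at f = 40%. Comparing all 2014 with all 2018 patients removes selection by airway within a year, but dilutes a true effect. If the true OR is 2.33 with no selection or period effect, the all-2014 rate is (114 × 0.30 + 28 × 0.4996)/142 = 33.9%, giving OR 1.94 and power about 65%. With 76 such patients it is 38.0%, giving OR 1.63 and power about 44%.

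**The case against.** The primary objective is worded as describing rates, and the sentence in section 4.7 is conditional background. That softens the point but does not remove it, because sections 11.1 and 11.2 power and test the difference.

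The existence of 2014 tracheostomy patients is inferred from section 6.1. No count is given, there may be very few, and some non-intubated patients may have had neither airway. Likewise, complete tracheostomy uptake in 2018 rests on the description of current practice; no 2018 figure is given, and section 7.1 still requires a tracheostomy in that year. Both caveats stand.

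Several stronger readings are tempting and go too far:

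- *The bias must favour intubation.* The documents never say that 2014 tracheostomy patients were at higher HAP risk. At 20% risk the spurious OR falls below 1, and the 40.9% figure needs a 60% risk and a 40% share together.
- *The dropped patients would separate airway from period.* They would make the two terms estimable, but they were themselves selected, so a within-2014 contrast still carries case selection.
- *Regression cannot help.* Wide variation in selection suggests overlap between the 2014 groups, and section 10.1 collects a reasonable set of covariates. Adjustment can deal with the measured part; the plan does not state it.
- *If the all-patients comparison points the same way, the difference is due to airway.* That comparison remains fully confounded with period and surgeon. With no airway effect it points to more HAP in 2018 about 50% of the time by chance, and about 92% of the time under a period OR of 1.5 from a 33% baseline.

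**Conclusion.** The concern holds as a statement about structure. The rules compare a selected part of 2014 with a 2018 cohort in which tracheostomy was routine; airway is inseparable from year and surgeon in the retained data; and no adjustment of the tested contrast is stated. This follows from sections 6.1, 7.1, 7.2, 11.1 and 11.2 read together, and section 7 contradicts section 6.1 on whether any 2014 patient had a tracheostomy.

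The size and direction of the bias cannot be determined from the documents. With an assumed 20-40% tracheostomy share in 2014 and no airway effect, the spurious OR runs from 1.15 to 1.31 at an assumed 45% risk and from 0.91 to 0.82 at 20%. A reader might infer that selection alone could produce the planned OR of 2.33. Nothing in the ranges tried supports that, though selection would add to, or offset, any period or surgeon effect. The plan should be changed before data are extracted.

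**What to change.** 1. **Eligibility.** Amend sections 7, 7.1 and 7.2 to include all consecutive maxillofacial resection and free flap patients from 2014 and from 2018, with the airway actually used recorded. Report how many had a tracheostomy in 2014. Reconcile section 7's statement about 2014 with section 6.1, and its use of 2017 as the tracheostomy year with the 2018 dates in section 7.1.
2. **Analysis.** Keep the 2014-intubated versus 2018-tracheostomy contrast, adjusted for pre-specified covariates already collected, for example smoking, respiratory history and tumour size. Add all-2014 versus all-2018 as a supporting analysis free of within-year airway selection. Show 2014-tracheostomy versus 2018-tracheostomy descriptively only, because it mixes period with case mix.
3. **Interpretation.** State that period and surgeon remain confounded with airway, so a difference is reported as an association between cohorts. Do not adopt a rule that attributes it to airway because the all-patients comparison agrees in direction.

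**Cost.** Section 7 already screens consecutive notes, so the extra work is full extraction for the added patients. For 2014 that is about 28 at a 20% share or 76 at 40%; the latter is 76/193 = 39% more, for one person with about two months (section 10.1). The all-patients comparison dilutes a true effect, and the tracheostomy-only comparison will be imprecise. Adjustment also costs power: if the covariates explain 10%, 20% or 30% of the variance of the cohort indicator, 193/(1 − R²) rises to 215, 242 or 276, or power at 193 falls to about 76%, 71% or 65%.
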